Data Analysis for Drug Repurposing for Effective Alzheimer's Medicines – Pentoxifylline vs Cilostazol

NCT05635370

July 7, 2023

1. Comparison Details

a. Intended aim(s)

To evaluate the comparative risk of dementia onset between patients treated with Pentoxifylline versus cilostazol for peripheral artery disease (PAD).

b. Primary endpoint

Incident dementia (i.e., Alzheimer's disease, vascular dementia, senile, presenile, or unspecified dementia, or dementia in other diseases classified elsewhere).

2. Person responsible for implementation

[name]

3. Data Source(s)

Medicare, 2008-2018

4. Study Design Diagrams

[figure not shown]
[figure not shown]

Figure- Alternate analysis approaches

[figure not shown]
■■■ Included person-time
 ■■■ Excluded person-time

Provides 'on treatment' estimates for the outcome risk and addresses exposure person-time misclassification

Analysis 1

[figure not shown]

Analysis 3

[figure not shown]

Addresses reverse causation due to preferential treatment initiation related to unrecorded cognitive impairment at study start and informative-censoring

Analysis 2

Analysis 4

5. Cohort Identification

a. Cohort Summary

This study will employ a new user, active comparator, observational cohort study design comparing Pentoxifylline versus Cilostazol. The patients will be required to have continuous enrollment during the baseline period of 365 days before initiation of study drugs (cohort entry/index date). Follow-up for the outcome (dementia) differs between analyses. Follow-up begins the day after drug initiation (analysis 1, 3, 4); 180 days after drug initiation (analysis 2).

b. Key details regarding cohort creation

Index date:

- Day of initiation of new Pentoxifylline versus Cilostazol use

Inclusion criteria for analyses 1, 3, 4:

- Aged \geq 65 years on the index date
- 365 days enrollment in Medicare Parts A, B, and D with no HMO coverage prior to index date
- No use of Pentoxifylline versus Cilostazol, any time prior to index date (all available lookback approach with a minimum of 365 days)
- No diagnosis of dementia any time prior to and including index date
- No history of nursing home admission recorded in any time prior to and including index date
- At least two claims with peripheral artery disease diagnosis recorded in 365 days prior to index date (ICD-9 or ICD-10 codes)¹

Inclusion criteria for analysis 2:

- Aged \geq 65 years on the index date
- 365 days enrollment in Medicare Parts A, B, and D with no HMO coverage prior to index date
- No use of Pentoxifylline versus Cilostazol, any time prior to index date (all available lookback approach with a minimum of 365 days)
- No diagnosis of dementia any time prior to and including index date
- No history of nursing home admission recorded in any time prior to and including index date
- At least two claims with peripheral artery disease diagnosis recorded in 365 days prior to index date (ICD-9 or ICD-10 codes)¹

- 180-day continuous use of Pentoxifylline versus Cilostazol starting on the index date

c. Flowchart of the study cohort assembly

	Less Excluded Patients	Remaining Patients
All patients		23,466,175
Did not meet cohort entry criteria	-23,393,311	72,864
Excluded due to insufficient enrollment	-45,683	27,181
Excluded based on Dementia Exclusion	-6,100	21,081
Excluded based on Nursing Home Admission	-4,080	17,001
Excluded based on Peripheral artery disease Diagnosis	-4,524	12,477
Excluded anyone aged <65 at index	-2,079	10,398
Patients in Pentoxifylline group		1,701
Patients in Cilostazol group		8,697
Final cohort		10,398

6. Variables

a. Exposure-related variables:

Study drug:

The study exposure of interest is initiation of Pentoxifylline

Comparator:

Cilostazol

b. Covariates:

Demographics	
Age	Region
Gender	Calendar year of index date
Race	Low income subsidy

Dementia risk factors	
Diabetes	Depression
Obesity	Anxiety
Hypertension	Bipolar disorder
Coronary artery disease	Schizophrenia

Markers for healthy behavior, frailty, healthcare use	
Smoking	Number of hospitalizations
Mammography	Number of physician office visits
Colonoscopy	Number of serum creatinine tests ordered
Fecal occult blood test	Composite frailty score
Influenza vaccination	Number of C-reactive protein tests ordered
Pneumococcal vaccination	Osteoporosis
Herpes zoster vaccination	Fractures
Bone mineral density test	Falls
Number of distinct generic agents	Use of supplemental oxygen
Number of emergency room visits	Combined comorbidity score
Number of outpatient visits	

Comedication use	
Lithium	Diuretics
Anti-epileptic mood stabilizers	Nitrates
Anti-epileptics (other than mood stabilizers)	Lipid lowering drugs

Atypical antipsychotics	Non-insulin diabetes medications
Benzodiazepines	Insulin
Serotonin-norepinephrine reuptake Inhibitors	Antidepressants
Selective serotonin reuptake inhibitors	Angiotensin II receptor blockers (ARBs)
Tricyclic antidepressants (TCAs)	Angiotensin converting enzyme inhibitors (ACEi)
Typical antipsychotics	Calcium channel blockers
Anticoagulants	Beta blockers
Antiplatelet agents	

Comorbid conditions	
Atrial fibrillation	Chronic liver disease
Coronary artery disease	Asthma
Heart failure	Ischemic heart disease
Stroke or transient ischemic attack	Chronic obstructive pulmonary disease
Peripheral vascular disease	Malignancy
Hyperlipidemia	Drug or alcohol abuse or dependence
Renal dysfunction	Venous thromboembolism
Rheumatoid Arthritis	Hypertension

Other PAD treatments and PAD severity indicators	
Critical limb ischemia Thrombolytic therapy (streptokinase, urokinase, alteplase, tissue plasminogen activator (tPA), pro-urokinase, reteplase, tenecteplase and Staphylokinase)	Number of cardiologist visits Number of hospitalizations with PAD

ICD-9, ICD-10, HCPCS, and NDC codes used to define the covariates listed above are available in Appendix A.

c. Outcome variables and study follow-up:

- **Primary outcome:** incident dementia, i.e., Alzheimer's disease, vascular dementia, senile, presenile, or unspecified dementia, or dementia in other diseases classified elsewhere. Outcome will be defined by 1 inpatient

claim or 2 outpatient claims in analysis 1, 2, 3. In analysis 4, the outcome will be defined by 1 inpatient or 1 outpatient claims and 1 prescription claim for a symptomatic treatment [donepezil, galantamine, rivastigmine, and memantine] within 6 months of each other with outcome date assigned to second event in the sequence.

- Secondary outcomes: Individual component:

Alzheimer's disease

Condition	ICD-9 and ICD-10 codes
Alzheimer's disease	331.0*, F00*, G30*
Vascular dementia	290.4*, F01*
Senile, presenile, or unspecified dementia	290.0*, 290.1*. 290.3*, 797*, F03*
Dementia in other diseases classified elsewhere	331.1*, 331.2*, 331.7*, 294.1*, F02*

For analysis 1,3, and 4 the follow-up will start the day after initiation of Pentoxifylline and Cilostazol and will continue until the earliest date of the following events:

- The first occurrence of the outcome of interest
- The date of end of continuous registration in the database,
- End of the study period,
- Measured death event occurs,
- The date of drug discontinuation, defined as the date of the last continuous treatment episode of the index drug (Pentoxifylline and Cilostazol) plus a defined grace period (i.e., 90 days after the end of the last prescription's days' supply in main analyses).

For analysis 2, the follow-up will start 180 days after initiation of Pentoxifylline and Cilostazol and will continue until the earliest date of the following events:

- The first occurrence of the outcome of interest, unless otherwise specified for selected outcomes,
- The date of end of continuous registration in the database,
- End of the study period,
- Measured death event occurs,
- Maximum allowed follow-up time (1095 days) reached

7. Propensity score analysis

We will use a propensity-score (PS)²-based approach to account for measured confounding in this study. The PS will be calculated as the predicted probability of initiating the exposure of interest (i.e., the repurposing candidate) versus the reference drug conditional on baseline covariates using multivariable logistic regression constructed separately in each data source. On average, patients with similar PSs have similar distribution of potential confounders used to estimate the PS. Therefore, analyses conditioned on the PS provide effect estimates that are free from measured confounding. For all our analyses, initiators of each exposure of interest will be matched with initiators of the reference exposure based on their PS within each data source.³ Pair matching will be conducted using a nearest-neighbor algorithm, which seeks to minimize the distance between propensity scores in each pair of treated and reference patients,⁴ and a caliper of 0.025 on the natural scale of the PS will be used to ensure similarity between the matched patients.⁵

We report multiple diagnostics for PS analysis in this protocol. First, the PS distributional overlap is provided between two groups before and after matching to ensure comparability of these groups.⁶ Next, balance in each individual covariate between two treatment groups is reported using standardized differences.⁷

8. Table for covariate balance

Variable	Crude			PS-Matched		
	Pentoxifylline (N = 1,701)	Cilostazol (N = 8,697)	St. Diff	Pentoxifylline (N = 1,687)	Cilostazol (N = 1,687)	St. Diff
Demographics						
Age, mean (SD)	76.2 (7.3)	75.3 (6.9)	0.13	76.2 (7.2)	76.3 (7.2)	-0.01
Gender, n (%)						
Male	828 (48.7)	4733 (54.4)	-0.12	822 (48.7)	827 (49)	-0.01
Female	873 (51.3)	3964 (45.6)	0.12	865 (51.3)	860 (51)	0.01
Race, n (%)						
White	1386 (81.5)	7096 (81.6)	0.00	1377 (81.6)	1347 (79.8)	0.05
Black	156 (9.2)	935 (10.8)	-0.05	156 (9.2)	176 (10.4)	-0.04
Hispanic	70 (4.1)	237 (2.7)	0.08	67 (4)	65 (3.9)	0.01
Other	89 (5.2)	429 (4.9)	0.01	87 (5.2)	99 (5.9)	-0.03
Region, n (%)						
Northeast; n (%)	274 (16.1)	1697 (19.5)	-0.09	272 (16.1)	288 (17.1)	-0.03
South; n (%)	795 (46.7)	3749 (43.1)	0.07	788 (46.7)	779 (46.2)	0.01
Midwest; n (%)	354 (20.8)	2069 (23.8)	-0.07	353 (20.9)	337 (20)	0.02
West; n (%)	273 (16)	1171 (13.5)	0.07	269 (15.9)	279 (16.5)	-0.02
Other; n (%)	5 (0.3)	11 (0.1)	0.04	5 (0.3)	4 (0.2)	0.01
Calendar year of index date, n (%)						
2014	444 (26.1)	2016 (23.2)	0.07	436 (25.8)	435 (25.8)	0.00
2015	338 (19.9)	1908 (21.9)	-0.05	336 (19.9)	310 (18.4)	0.04
2016	335 (19.7)	1713 (19.7)	0.00	335 (19.9)	349 (20.7)	-0.02
2017	303 (17.8)	1606 (18.5)	-0.02	300 (17.8)	296 (17.5)	0.01

DREAM study protocol - Comparison 12 Pentoxifylline vs Cilostazol

2018	281 (16.5)	1454 (16.7)	-0.01	280 (16.6)	297 (17.6)	-0.03
Low income subsidy, n (%)	464 (27.3)	2035 (23.4)	0.09	459 (27.2)	492 (29.2)	-0.04
Dementia risk factors, n (%)						
Anxiety	247 (14.5)	1090 (12.5)	0.06	245 (14.5)	236 (14)	0.02
Bipolar disorder	15 (0.9)	67 (0.8)	0.01	15 (0.9)	13 (0.8)	0.01
Coronary artery disease	800 (47)	4789 (55.1)	-0.16	792 (46.9)	790 (46.8)	0.00
Depression	240 (14.1)	1027 (11.8)	0.07	236 (14)	226 (13.4)	0.02
Diabetes	826 (48.6)	4211 (48.4)	0.00	819 (48.5)	852 (50.5)	-0.04
Hypertension	1512 (88.9)	8055 (92.6)	-0.13	1500 (88.9)	1502 (89)	0.00
Obesity	325 (19.1)	1373 (15.8)	0.09	321 (19)	308 (18.3)	0.02
Schizophrenia	2 (0.1)	8 (0.1)	0.01			0.00
Markers for healthy behavior, frailty, healthcare use						
Bone mineral density test, n (%)	141 (8.3)	725 (8.3)	0.00	139 (8.2)	130 (7.7)	0.02
Colonoscopy, n (%)	143 (8.4)	861 (9.9)	-0.05	141 (8.4)	148 (8.8)	-0.02
Fecal occult blood test, n (%)	132 (7.8)	696 (8)	-0.01	131 (7.8)	131 (7.8)	0.00
Influenza vaccination, n (%)	1035 (60.8)	5419 (62.3)	-0.03	1026 (60.8)	978 (58)	0.06
Mammography, n (%)	281 (16.5)	1455 (16.7)	-0.01	279 (16.5)	283 (16.8)	-0.01
Pneumococcal vaccination, n (%)	652 (38.3)	3612 (41.5)	-0.07	649 (38.5)	621 (36.8)	0.03
Smoking, n (%)	599 (35.2)	3881 (44.6)	-0.19	595 (35.3)	580 (34.4)	0.02
Number of C-reactive protein tests ordered, mean (SD)	0.3 (1.2)	0.2 (0.7)	0.13	0.3 (0.9)	0.3 (1)	-0.02
Number of emergency room visits, mean (SD)	0.8 (1.4)	0.7 (1.3)	0.08	0.7 (1.4)	0.7 (1.4)	0.00
Number of distinct prescriptions, mean (SD)	13.9 (6.7)	12.4 (5.9)	0.23	13.7 (6.6)	13.8 (6.7)	0.00

DREAM study protocol - Comparison 12 Pentoxifylline vs Cilostazol

Number of hospitalizations, mean (SD)	0.3 (0.7)	0.2 (0.6)	0.09	0.3 (0.7)	0.3 (0.6)	0.01
Number of outpatient visits, mean (SD)	15 (10.6)	13.1 (8.6)	0.20	14.8 (10.1)	14.9 (10)	-0.01
Number of serum creatinine tests ordered, mean (SD)	1.6 (2.7)	1.5 (2.3)	0.01	1.6 (2.7)	1.5 (2.2)	0.02
Composite frailty score, mean (SD)	0.2 (0.1)	0.2 (0.1)	0.21	0.2 (0.1)	0.2 (0.1)	0.02
Falls, n (%)	107 (6.3)	472 (5.4)	0.04	107 (6.3)	108 (6.4)	0.00
Fractures, n (%)	141 (8.3)	591 (6.8)	0.06	139 (8.2)	138 (8.2)	0.00
Osteoporosis, n (%)	247 (14.5)	1051 (12.1)	0.07	242 (14.3)	239 (14.2)	0.01
Use of supplemental oxygen, n (%)	26 (1.5)	150 (1.7)	-0.02	26 (1.5)	23 (1.4)	0.02
Combined comorbidity score, mean (SD)	3.4 (2.8)	2.9 (2.4)	0.18	3.3 (2.7)	3.4 (2.6)	-0.02
Comedication use, n (%)						
Angiotensin converting enzyme inhibitors (ACEi)	646 (38)	3657 (42)	-0.08	643 (38.1)	641 (38)	0.00
Angiotensin II receptor blockers (ARBs)	488 (28.7)	2519 (29)	-0.01	485 (28.7)	482 (28.6)	0.00
Antidepressants	435 (25.6)	2046 (23.5)	0.05	430 (25.5)	416 (24.7)	0.02
Beta blockers	894 (52.6)	4801 (55.2)	-0.05	887 (52.6)	884 (52.4)	0.00
Calcium channel blockers	593 (34.9)	3243 (37.3)	-0.05	588 (34.9)	590 (35)	0.00
DMARD	86 (5.1)	212 (2.4)	0.14	80 (4.7)	81 (4.8)	0.00
Diuretics	930 (54.7)	4251 (48.9)	0.12	918 (54.4)	925 (54.8)	-0.01
Insulin	228 (13.4)	1176 (13.5)	0.00	224 (13.3)	216 (12.8)	0.01
Lipid lowering drugs	1169 (68.7)	6557 (75.4)	-0.15	1161 (68.8)	1151 (68.2)	0.01
Nitrates	239 (14.1)	1355 (15.6)	-0.04	233 (13.8)	225 (13.3)	0.01

DREAM study protocol - Comparison 12 Pentoxifylline vs Cilostazol

Non-insulin diabetes medications	477 (28)	2493 (28.7)	-0.01	473 (28)	481 (28.5)	-0.01
Anticoagulants	218 (12.8)	814 (9.4)	0.11	212 (12.6)	190 (11.3)	0.04
Anti-epileptic mood stabilizers	20 (1.2)	94 (1.1)	0.01	20 (1.2)	17 (1)	0.02
Antiplatelet agents	411 (24.2)	8697 (100)	-2.51			0.00
Atypical antipsychotics	25 (1.5)	102 (1.2)	0.03	25 (1.5)	22 (1.3)	0.02
Benzodiazepines	352 (20.7)	1416 (16.3)	0.11	347 (20.6)	331 (19.6)	0.02
Lithium	2 (0.1)	14 (0.2)	-0.01			0.00
Anti-epileptics (other than mood stabilizers)	459 (27)	2073 (23.8)	0.07	455 (27)	457 (27.1)	0.00
Serotonin-norepinephrine reuptake inhibitors	83 (4.9)	361 (4.2)	0.04	82 (4.9)	75 (4.4)	0.02
Selective serotonin reuptake inhibitors	222 (13.1)	1141 (13.1)	0.00	221 (13.1)	221 (13.1)	0.00
Tricyclic antidepressants (TCAs)	77 (4.5)	320 (3.7)	0.04	75 (4.4)	63 (3.7)	0.04
Typical antipsychotics	8 (0.5)	20 (0.2)	0.04	8 (0.5)	10 (0.6)	-0.02
Other PAD treatments and PAD severity indicators , n (%)						
Critical limb ischemia	394 (23.2)	1058 (12.2)	0.29	381 (22.6)	380 (22.5)	0.00
Thrombolytic therapy	10 (0.6)	26 (0.3)	0.04	9 (0.5)	6 (0.4)	0.03
Number of cardiologist visits, mean (SD)	3.5 (5.9)	4 (5.2)	-0.08	3.5 (5.9)	3.5 (4.9)	-0.01
Number of hospitalizations with PAD, mean (SD)	0 (0.1)	0 (0.2)	-0.04	0 (0.1)	0 (0.1)	0.01
Comorbid conditions, n (%)						
Atrial fibrillation	296 (17.4)	1195 (13.7)	0.10	290 (17.2)	296 (17.5)	-0.01

DREAM study protocol - Comparison 12 Pentoxifylline vs Cilostazol

Chronic obstructive pulmonary disease	557 (32.7)	2821 (32.4)	0.01	550 (32.6)	556 (33)	-0.01
Chronic liver disease	91 (5.3)	591 (6.8)	-0.06	89 (5.3)	89 (5.3)	0.00
Drug or alcohol abuse or dependence	282 (16.6)	2134 (24.5)	-0.20	281 (16.7)	284 (16.8)	-0.01
Heart failure	336 (19.8)	1320 (15.2)	0.12	329 (19.5)	335 (19.9)	-0.01
Hyperlipidemia	1309 (77)	7176 (82.5)	-0.14	1300 (77.1)	1303 (77.2)	0.00
Ischemic heart disease	792 (46.6)	4714 (54.2)	-0.15	784 (46.5)	783 (46.4)	0.00
Malignancy	508 (29.9)	2426 (27.9)	0.04	502 (29.8)	517 (30.6)	-0.02
Peripheral vascular disease	1646 (96.8)	8451 (97.2)	-0.02	1634 (96.9)	1635 (96.9)	0.00
Rheumatoid Arthritis	112 (6.6)	348 (4)	0.12	108 (6.4)	100 (5.9)	0.02
Renal dysfunction	478 (28.1)	2178 (25)	0.07	471 (27.9)	478 (28.3)	-0.01
Stroke or transient ischemic attack	241 (14.2)	1170 (13.5)	0.02	236 (14)	242 (14.3)	-0.01
Venous thromboembolism	132 (7.8)	410 (4.7)	0.13	128 (7.6)	125 (7.4)	0.01

9. Statistical analysis plans

Incidence rates for the outcome will be estimated for the treatment and reference groups before and after PS matching. The competing risk of death could be of concern for the current set of analyses if mortality is frequent among patients included in the cohort and if differences in the risk of mortality between treatment and reference groups are substantial. In the PS-matched sample, we will use cause-specific hazard models⁸ to provide hazard ratios averaged over the entire follow-up period as well as interval specific hazard ratios (1, 2, and 3 years) for the association between the treatment of interest and risk of ADRD after considering all-cause mortality as a competing event. Pre-specified subgroup analyses will be conducted based on age, sex, and baseline cardiovascular disease.

10. References

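### Do index dates confined to 2014-2018 conflict with a data source described as Medicare 2008-2018?

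*Combined protocol and SAP*

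**What the plan says.** Section 3 names the source and span in one line: "Medicare, 2008-2018". Section 5b makes the index date the day a patient newly starts either drug. It asks for 365 days of enrolment in Parts A, B and D, and for no earlier use of the study drugs under an "all available lookback approach with a minimum of 365 days". Recorded dementia or nursing-home admission at any point up to the index date excludes the patient. Neither eligibility list (analyses 1, 3 and 4; analysis 2) mentions a calendar window.

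The flowchart in section 5c starts with a single un-itemised step, "Did not meet cohort entry criteria", which removes 23,393,311 of 23,466,175 people. No later step concerns calendar time. The section 8 block headed "Calendar year of index date, n" (%) has five rows, 2014 to 2018. Section 6c censors at "End of the study period" without a date beside it, and analysis 2 adds a cap, "Maximum allowed follow-up time (1095 days) reached". Section 9 plans hazard ratios at 1, 2 and 3 years. Section 4 holds the study design diagrams, which are not visible in the text reviewed.

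**The concern.** Read literally, data from 2008 with a one-year minimum history admit initiators from about the start of 2009, but no patient entered before 2014. Three explanations come to mind:

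- Eligible 2009-2013 initiators were left out. Up to five accrual years would then be unused, in a study where pentoxifylline is the limiting arm and 1,687 of its 1,701 patients are already matched.
- The years 2008-2013 were kept for lookback only. Nothing is then wrong except that the readable text does not say so.
- The data actually used begin around 2013. Section 3 would then be inaccurate, and the exclusions for prior use, dementia and nursing-home stay would rest on only one to two years of history for 2014 initiators. In a study of incident dementia that would weaken the claim that patients were new users and free of disease.

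The entry window also fixes how many patients can be followed into the third year, for which a separate hazard ratio is planned.

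**Working it through.** **Do the index-year rows account for everyone?** Inputs are the section 8 rows for 2014 to 2018 and the arm totals in sections 5c and 8.

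- Crude pentoxifylline: 444 + 338 + 335 + 303 + 281 = 1,701.
- Crude cilostazol: 2,016 + 1,908 + 1,713 + 1,606 + 1,454 = 8,697.
- Total: 1,701 + 8,697 = 10,398, the final cohort in section 5c.
- Matched pentoxifylline: 436 + 336 + 335 + 300 + 280 = 1,687.
- Matched cilostazol: 435 + 310 + 349 + 296 + 297 = 1,687.

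Nobody is left over, so a dropped table row cannot hide earlier entrants. The flowchart also subtracts correctly: 23,466,175 → 72,864 → 27,181 → 21,081 → 17,001 → 12,477 → 10,398.

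**What do the written rules admit?** Assuming data start on 1 January 2008, adding 365 days gives a first admissible index date of 31 December 2008. The gap to 2014 is therefore real on the page.

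**Does that make the sections contradictory?** Section 3 describes which data exist. Section 5b describes how far back to look, namely as far as the data go. Section 8 describes when patients entered. An unlimited lookback has substance only if the data begin well before entry:

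- Data start 1 January 2008, index in 2014: 6.0 to 7.0 years of possible history.
- Data start 1 January 2013 (assumption), index in 2014: 1.0 to 2.0 years.
- Data start 1 January 2008, index in 2009: again 1.0 to 2.0 years.

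The first line agrees with all three sections as written. The second requires section 3 to be false. The third shows the price of adding the earliest years: those entrants would have the same short history that would be a weakness under the second.

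**Is there a between-arm consequence?** The matched standardised differences for index year are 0.00, 0.04, -0.02, 0.01 and -0.03, so the largest in absolute value is 0.04. Calendar time does not separate the arms.

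**Follow-up ceiling.** Matched patients by year, both arms, are 871, 646, 684, 596 and 577, total 3,374. Assume data end on 31 December 2018, entry is uniform within each year and there is no other censoring.

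- One year possible: (871 + 646 + 684 + 596) / 3,374 = 2,797 / 3,374 = 82.9%.
- Able to enter the third year: (871 + 646 + 684) / 3,374 = 2,201 / 3,374 = 65.2%.
- Able to complete 1,095 days (index by 1 January 2016): about 1,519 / 3,374 = 45.0%.

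These are upper bounds. They describe ordinary administrative censoring of a 2014-2018 cohort and are the same whether 2008-2013 was held for lookback or never held. They do not measure any mismatch.

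**The case for a change.** The strongest case for acting is that the possible explanations describe different studies and the readable text does not choose between them. The operative eligibility lists, given in full twice, contain no dates. The strength of the any-time-prior exclusions depends on when the data begin. Crude pentoxifylline initiations fall from 444 in 2014 to 338 in 2015 (106/444 = 24%), while cilostazol falls from 2,016 to 1,908 (108/2,016 = 5%). A reader unsure of the data start might wonder whether some 2014 new users were returning users.

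Part of this stands: the readable text gives neither the entry window nor the exact end date. The rest does not carry far. The fall in pentoxifylline may be a real trend and says nothing about lookback. The two harmful explanations have no supporting passage; one supposes that eligible patients were dropped, the other that section 3 is wrong. The window may be drawn in the section 4 diagrams or applied in the first flowchart step. A figure lost in text extraction is not a gap in the plan. The end of study is not open either: section 3 stops the data in 2018 and the last index year is 2018, so only the day is missing.

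Lost precision cannot be sized, because no pre-2014 counts are given. Adding those years would also shorten the lookback for the earliest entrants. Reporting numbers at risk by interval is sensible practice, but it is a separate matter from this one.

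**Conclusion.** No change follows. The row sums are certain: all 10,398 crude and all 3,374 matched index dates fall in 2014-2018, and section 5b states no calendar limit in the readable text. That is an unstated detail, not a demonstrated error. The reading that fits sections 3, 5b and 8 together is that the earlier years serve as lookback, which is how an analyst would normally take a data span paired with an all-available-history rule. Under it the cohort, the matching and the hazard models stay exactly as planned, and index-year balance (at most 0.04 after matching) leaves no route to between-arm bias.

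This conclusion assumes that section 3 is accurate about the data held. If 2008-2013 data were in fact not used, section 3 would need correcting and the exclusions would be weaker for 2014 entrants, but no passage suggests this. Extending entry back to 2009 would exchange depth of history for an unknown number of patients, and the documents give no basis for preferring that trade.

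### Original reason for Medicare entitlement is in neither the propensity score nor the balance table, although most 65-year-olds and an unknown share of older patients were enrolled before 65

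*Combined protocol and SAP*

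**What the plan says.** Both inclusion lists in section 5b (analyses 1, 3 and 4, and analysis 2) require patients to be at least "65 years on the index date" and to have "365 days enrollment in Medicare Parts A, B, and D with no HMO coverage prior to index date". Section 5a adds that this must be "continuous enrollment during the baseline period of 365 days before initiation of study drugs".

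The last exclusion in the section 5c flowchart, "Excluded anyone aged <65 at index", removes 2,079 of the 12,477 patients who had passed every other step, including enrolment. It leaves 10,398: 1,701 on pentoxifylline and 8,697 on cilostazol.

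The demographic covariates in section 6b are age, gender, race, region, calendar year and "Low income subsidy". Reason for entitlement is not among them and has no row in the section 8 balance table. ESRD has no flag of its own in either place; the nearest item is a single renal dysfunction variable. Section 7 bases confounding control on matching by a propensity score built from the listed covariates. Section 9 adds: "Pre-specified subgroup analyses will be conducted based on age, sex, and baseline cardiovascular disease". It gives no age cut-points.

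**The concern.** A patient who qualifies for Medicare by age alone can hardly have a full prior year of cover while still 65. The two entry rules therefore select, at the youngest age, mainly people who were already enrolled. They also let in every older patient who first joined before 65.

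If early enrolment reflects disability or ESRD, it marks long-standing serious illness that could plausibly affect dementia risk, death and drug stopping, and perhaps the choice between the two drugs. Among patients aged 66 and over, entitlement varies at any given age, so balancing age does not balance it. The study relies on measured covariates for confounding control, and a reader of section 8 cannot see whether this one differs between the matched groups.

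**Working it through.** **1. The plan's own figures.** Every flowchart subtraction is exact, and the last gives 12,477 − 2,079 = 10,398 = 1,701 + 8,697. Share under 65 among otherwise eligible initiators: 2,079 / 12,477 = 16.7%. The tabulated standardised differences also reproduce. For low income subsidy, (p1 − p0) / √[(p1q1 + p0q0)/2] gives 0.089 crude and −0.043 matched, against 0.09 and −0.04 in section 8.

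**2. Date logic.** Age at index in [65, 66) minus 365 days gives age in [64, 65). Over all combinations of birth date and index date at age 65, 99.8% need enrolment to start before the 65th birthday; the remainder is a leap-day effect. If age-based cover is assumed to start on the first of the birthday month, the figure is 95.5%. That leaves a window f = 0.045 in which age-entitled people can qualify.

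**3. Share of 65-year-olds who enrolled early.** With d the early-entitled share of potential initiators at that age (assumed), the share among those eligible is d / [d + (1 − d)f]:

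| d | Early-entitled among eligible 65-year-olds |
|---|---|
| 10% | 71% |
| 16.7% | 82% |
| 25% | 88% |
| 40% | 94% |

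So most, but not all.

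**4. Size of the group.** The documents give no count at age 65. If 5–12% of the 2,079 were aged 64 and about as many are aged 65, that is 104–249 patients, or 1.0–2.4% of 10,398. Fitting skewed age distributions to the tabulated means and SDs gives about 0.6–4.7% of an arm. If the number falls 4–8% per further year of age up to 90, those who first enrolled before 65 at any age number:

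- 1,151–1,700 (11–16% of the cohort) from a 5% starting share;
- 1,841–2,719 (18–26%) from 8%;
- 2,762–4,079 (27–39%) from 12%.

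All of these follow from assumed inputs.

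**5. Related covariates, pentoxifylline v cilostazol (section 8).**

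| Covariate | Crude | Matched | Matched St. Diff |
|---|---|---|---|
| Low income subsidy | 27.3% v 23.4% | 27.2% v 29.2% | −0.04 |
| Renal dysfunction | 28.1% v 25.0% | 27.9% v 28.3% | −0.01 |
| Depression | 14.1% v 11.8% | 14.0% v 13.4% | 0.02 |
| Comorbidity score | 3.4 v 2.9 | 3.3 v 3.4 | −0.02 |
| Frailty score | 0.2 v 0.2 (St. Diff 0.21) | 0.2 v 0.2 | 0.02 |

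**6. Possible bias.** Factor on the hazard ratio = [1 + p1(R − 1)] / [1 + p0(R − 1)], where p1 and p0 are the early-entitled shares on pentoxifylline and cilostazol and R is the dementia hazard ratio for early entitlement.

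- Gaps as in the three matched binary proxies (+0.6, −0.4 and −2.0 points), p0 = 0.12–0.25, R = 1.3–2.0: about 0.98 to 1.005. For example, p0 = 0.12, p1 = 0.10, R = 2 gives 1.10 / 1.12 = 0.982.
- Residual gap of 2–4 points, same p0 and R: 1.006 to 1.036. This gap is about the size of the crude proxy gaps (2.3, 3.1 and 3.9 points), as if matching had removed nothing.
- Gap of 2–5 points, p0 = 0.10–0.20, R = 1.5–3: 1.009 to 1.083. The upper end needs a residual gap larger than any of those crude proxy gaps, together with R = 3.

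**The case against.** The strongest counter-argument is that little is left to confound. If nearly all 65-year-olds enrolled early, entitlement barely varies at that age, so it cannot confound within it. Age itself is in the score and balanced on its mean (76.2 v 76.3, standardised difference −0.01). Frailty, comorbidity, renal dysfunction, psychiatric diagnoses, subsidy and healthcare use are all matched and reported. This largely stands. It confines the concern mainly to patients aged 66 and over, and makes a large residual imbalance unlikely. It does not close the point, because balance on proxies is not evidence of balance on an unlisted variable, and a balanced mean age does not show balance at the youngest ages.

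A reader might infer that the hazard ratio is biased against pentoxifylline, because several illness markers are higher in that group before matching. The documents do not support this. Section 9 estimates hazard ratios in the matched sample, where the gaps are near zero and, for subsidy, reversed. Even the crude data are mixed: drug or alcohol abuse (16.6% v 24.5%), smoking (35.2% v 44.6%) and coronary artery disease (47% v 55.1%) are lower with pentoxifylline, whose initiators are also older (76.2 v 75.3).

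A reader might also infer that the youngest age subgroup is essentially a disability subgroup. Section 9 sets no cut-points, and in a broad band the 65-year-olds would be diluted.

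**Conclusion.** The gap is real but modest. The entry rules bring in patients enrolled before 65, the flowchart shows that such patients are numerous just below the age limit, and the variable that identifies them is neither directly balanced nor reported. It would go too far to call the group wholly unbalanced, since close correlates are matched to within 0.04.

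Any residual bias is probably small, at most a few percent on the hazard ratio, with unknown direction. That rests on assumed values for the size of the group, its residual imbalance and its dementia risk. The link from early enrolment to disability or ESRD is also an assumption, as is the higher risk; the documents establish only that early enrollees exist. The case for acting is that the omission is cheap to close in a study whose stated confounding control is matching on measured covariates. It does not show that the result is wrong.

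**What to change.** If the enrolment file carries the code (assumed, not stated), add original reason for entitlement (age; disability; ESRD; both) to the section 6b demographics. Re-estimate the propensity score, re-match, and add the row to the section 8 balance table.

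As a sensitivity check, report the hazard ratio once in age-entitled patients. Restricting to age 66 and over is a simpler alternative, but it removes only the 65-year-olds and leaves in older patients who enrolled early. Raising the minimum age in the main analysis is optional; the added covariate addresses the confounding path without it.

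The cost is one more covariate, one re-run of the matching and a smaller sample in the sensitivity check. An age-66 restriction would lose about 1–2% of patients under the assumptions above; the loss from restricting to age-entitled patients would be larger and cannot be fixed from the documents (11–26% under the 5–8% starting shares, up to 39% in the extreme case). No new data source is needed if the code is available.
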